TIA/CVA	All grades	Permanently discontinue both drugs	Any new CVA event confirmed by MRI with diffusion weighted imaging, regardless of neurological symptoms (eg, cryptogenic CVA) and for suspected TIA without clear alternative etiology. See Appendix 7 .

Abbreviations: AE, adverse event; CVA, cerebrovascular accident; TIA, transient ischemic attack.

^a If dosing of one drug is delayed, then dosing of both drugs is delayed.

***Per Protocol Amendment 04, participants are required to discontinue bempegaldesleukin and may continue on nivolumab treatment.** Advanced Cardiac Life Support (ACLS) and institutional guidelines should be followed for all CVA cases. For participants previously treated with bempegaldesleukin plus nivolumab who have a CVA or TIA, the Investigator should discuss risk/ benefit of continuing nivolumab. The managements algorithm for CVA or TIA ([Appendix 7](#)) is not applicable per Protocol Amendment 04.

7.4.1.1 Dose Modification Criteria for Bempegaldesleukin and Nivolumab for Cycle 1 AST/ALT Elevations

This section is not applicable per Protocol Amendment 04. These recommendations are for Cycle 1 only and are not intended to serve as rigid guidelines or to replace clinical judgement. Subsequent cycles should follow standard Hepatic Adverse Event Management Algorithm ([Appendix 6](#)).

Rule out alternative etiologies. Consider imaging if obstruction is suspected. If there is a non-inflammatory etiology, treat accordingly and continue bempegaldesleukin and nivolumab.

If ALT/AST increases during monitoring, follow the guidance for the highest levels.

AST or ALT > 3.0 to $\leq 5 \times$ ULN (within first cycle of bempegaldesleukin + nivolumab)

Increase frequency of liver function test (LFT) monitoring to approximately every 3 days and delay treatment until lab abnormalities resolve to Grade 1 or baseline.

If no improvement within 7 days, treat with 0.5-1 mg/kg/day prednisone equivalents, and taper steroids over at least 1 month before resuming treatment.

ALT or AST > 5.0 to $\leq 8.0 \times$ ULN (within first cycle of bempegaldesleukin + nivolumab)

Increase frequency of monitoring to approximately every 3 days until lab abnormalities resolve to Grade 1 or baseline.

Treatment must be delayed until lab abnormalities resolve to Grade 1 or baseline.

If no improvement within 7 days (follow Hepatic Adverse Event Management Algorithm [[Appendix 6](#)]);

- Discontinue bempegaldesleukin + nivolumab
- 1 to 2 mg/kg/day prednisone equivalents followed by corticosteroid taper over at least one month
- Consult gastroenterologist
- Consider adding non-corticosteroid immunosuppressive medication if no improvement in > 3-5 days, worsens or rebounds while on steroids

ALT or AST > $8.0 \times$ ULN (follow Hepatic Adverse Event Management Algorithm [[Appendix 6](#)])

- Discontinue bempegaldesleukin + nivolumab
- Increase frequency of monitoring to approximately 1-2 days
- 1 to 2 mg/kg/day prednisone equivalents followed by corticosteroid taper over at least one month
- Consult gastroenterologist
- If no improvement in > 3–5 days, worsens or rebounds, add non-corticosteroid immunosuppressive medication

Please refer to [Section 8.1](#) for discontinuation criteria.

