AE criteria for delaying, resuming, and discontinuing nivolumab and bempegaldesleukin are available in [Table 7.4.1-1](#) and [Section 8.1.1](#). Participants may resume treatment with study drug if they have completed AE management (ie, corticosteroid taper) or are on ≤ 10 mg prednisone or equivalent.

Participants who require delay of nivolumab should be re-evaluated weekly or more frequently if clinically indicated and resume nivolumab dosing when re-treatment criteria are met. Dose reductions for nivolumab are not permitted in this study.

Not applicable per Protocol Amendment 04. Dose delays and reductions are permitted for bempegaldesleukin. Bempegaldesleukin may be delayed or reduced to 0.003 mg/kg based on observed drug-related toxicities. If the bempegaldesleukin dose is reduced to 0.003 mg/kg, the dose level should remain at this level throughout the remainder of the study and will not be re-escalated.

Not applicable per Protocol Amendment 04. Bempegaldesleukin dosing may resume at the same bempegaldesleukin dose or at a lower bempegaldesleukin dose level when toxicity resolves to Grade 1 or returns to baseline, except for instances where the potential recurrence of the event poses an undue risk for the participant. Medical Monitor consultation is required for dose reduction.

Table 7.4.1-1: Adverse Event Criteria for Delay, Resumption, and Discontinuation of Nivolumab and Bempegaldesleukin (if One is Delayed, Both Delayed) *Per Protocol Amendment 04, the text below related to bempegaldesleukin is not applicable; however, the criteria remain unchanged for nivolumab

Note: Bempegaldesleukin must be discontinued for participants receiving bempegdesleukin plus nivolumab			
Drug-related AE per CTCAE v5	Severity	Action Taken	Clarifications, Exceptions, and Resume Criteria
Gastrointestinal			
Colitis or Diarrhea	Grade 2	Delay dose	Dosing may resume when AE resolves to baseline.
	Grade 3	Delay dose	Dosing may resume when AE resolves to baseline.
	Grade 4	Permanently discontinue	
Renal			
Serum Creatinine Increased See bempegaldesleukin-specific criteria in Table 7.4.1-2 for transient, non-inflammatory increased serum creatinine.	Grade 2 or 3	Nivolumab: Delay dose ^a	Dosing may resume when AE resolves to Grade ≤ 1 or baseline value.
	Grade 4	Permanently discontinue	
Pulmonary			
Pneumonitis	Grade 2	Delay dose	Dosing may resume after pneumonitis has resolved to ≤ Grade 1.
	Grade 3 or 4	Permanently discontinue	

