Table 7.4.1-1: Adverse Event Criteria for Delay, Resumption, and Discontinuation of Nivolumab and Bempegaldesleukin (if One is Delayed, Both Delayed) *Per Protocol Amendment 04, the text below related to bempegaldesleukin is not applicable; however, the criteria remain unchanged for nivolumab

Note: Bempegaldesleukin must be discontinued for participants receiving bempegaldesleukin plus nivolumab			
Drug-related AE per CTCAE v5	Severity	Action Taken	Clarifications, Exceptions, and Resume Criteria
Hepatic			
AST, ALT, or T.bili Increased	AST or ALT > 3× and ≤ 5× ULN or T.bili > 1.5× and ≤ 3× ULN, regardless of baseline value	Delay dose	Dosing may resume when laboratory values return to baseline.
	AST or ALT > 5× ULN or T.bili > 3× ULN, regardless of baseline value	Permanently discontinue	ALT/AST elevations < 8.0 x ULN in Cycle 1 only, study treatment does not need to be discontinued (see Section 7.4.1.1 for dose modification criteria).
	Concurrent AST or ALT > 3× ULN and T.bili > 2× ULN, regardless of baseline value	Permanently discontinue	
Endocrinopathy			
Adrenal Insufficiency	Grade 2 adrenal insufficiency	Delay dose	Dosing may resume after adequately controlled with hormone replacement.
	Grade 3 or 4 adrenal insufficiency or adrenal crisis	Delay dose or permanently discontinue	Mandatory discussion with and approval from the Medical Monitor needed prior to resuming nivolumab/bempegaldesleukin therapy. If adrenal insufficiency resolves or is adequately controlled with physiologic hormone replacement, participant may not require discontinuation of nivolumab.

Table 7.4.1-1: Adverse Event Criteria for Delay, Resumption, and Discontinuation of Nivolumab and Bempegaldesleukin (if One is Delayed, Both Delayed) *Per Protocol Amendment 04, the text below related to bempegaldesleukin is not applicable; however, the criteria remain unchanged for nivolumab

Note: Bempegaldesleukin must be discontinued for participants receiving bempegaldesleukin plus nivolumab			
Drug-related AE per CTCAE v5	Severity	Action Taken	Clarifications, Exceptions, and Resume Criteria
Hyperglycemia	Hyperglycemia requiring initiation or change in daily management (Grade 2 or 3)	Delay dose	Dosing may resume if hyperglycemia resolves to Grade ≤ 1 or baseline value, or is adequately controlled with glucose-controlling agents.

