7.4.2 Monitoring and Management of Elevated Hepatic Transaminases

Per Protocol Amendment 04, language for bempegaldesleukin is no longer applicable. Elevated hepatic transaminases are an overlapping toxicity that can occur for both bempegaldesleukin and nivolumab. The elevations in hepatic transaminases associated with bempegaldesleukin typically occur at the time of peak active cytokine concentration in the blood (Days 2-4), and are often accompanied by other cytokine-related toxicities such as flu-like symptoms, rash or pruritus. The transient elevations in hepatic transaminases are usually mild or moderate in severity, not associated with increased total bilirubin, resolve spontaneously without treatment, and predominantly occur in Cycle 1 and Cycle 2. Grade 3 laboratory abnormalities with these characteristics have been observed in PIVOT-02 during Cycle 1, and participants were able to continue study treatment uninterrupted with close laboratory monitoring. For transaminase elevations occurring in Cycle 1 consistent with a cytokine related effect without alternative etiologies, follow the Cycle 1 hepatic adverse event management guideline ([Section 7.4.1.1](#)).

Hepatic events, including elevated liver function tests, have also been observed for nivolumab. Most cases were of low or moderate severity. Higher grade abnormalities are concerning for immune-mediated hepatitis, and typically occur with a later onset (median time to onset of 3.3 months). Immune-mediated hepatitis generally results in a quick rise in liver function tests, and responds to corticosteroids or immune-modulating agents. For transaminase elevations occurring in Cycle 2 onwards potentially involving an immune-mediated mechanism, follow the immune-mediated hepatic adverse event management guidelines in the nivolumab Investigator's Brochure or product labeling for appropriate management.

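### Amendment 04 withdrew Section 7.4.1.1 but left the Cycle 1 hepatic exception that depends on it unmarked in Table 7.4.1-1, so the ALT/AST stop rule for nivolumab alone has two readings in Cycle 1 (minor)

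*Combined protocol and SAP*

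**What the plan says.** The hepatic row of Table 7.4.1-1 has three tiers. AST or ALT above 3 and up to 5 x ULN calls for a dose delay. AST or ALT above 5 x ULN calls for permanent discontinuation, and so does AST or ALT above 3 x ULN together with total bilirubin above 2 x ULN. Bilirubin alone has its own limits in the first two tiers. Beside the second tier stands the exception: "ALT/AST elevations < 8.0 x ULN in Cycle 1 only, study treatment does not need to be discontinued", with a reference to Section 7.4.1.1. Section 8.1.1 makes the table's discontinuation criteria mandatory.

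The Amendment 04 banner on the table title reads "the text below related to bempegaldesleukin is not applicable; however, the criteria remain unchanged for nivolumab". Section 7.4.1.1 opens with "This section is not applicable per Protocol Amendment 04. These recommendations are for Cycle 1 only", and its bands up to 8 x ULN were limited to events "within first cycle of bempegaldesleukin + nivolumab".

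Section 7.4.2 has its own banner: "Per Protocol Amendment 04, language for bempegaldesleukin is no longer applicable". Below it, Cycle 1 elevations are routed to 7.4.1.1 if they are "consistent with a cytokine related effect without alternative etiologies, follow the Cycle 1 hepatic adverse event management guideline". The nivolumab paragraph then says "For transaminase elevations occurring in Cycle 2 onwards potentially involving an immune-mediated mechanism, follow the immune-mediated hepatic adverse event management guidelines". It names the Investigator's Brochure for nivolumab, or the label, as the source.

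**The concern.** A stop rule for a potentially serious toxicity should have one reading. Here an investigator seeing isolated ALT of 6 x ULN in Cycle 1 on nivolumab alone could conclude that nivolumab must be stopped for good, or that stopping is not required. Both conclusions come from the same cell.

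Section 7.4.2 gives the clinical reason for tolerating early elevations: transient cytokine effects of bempegaldesleukin. That drug is no longer given. For nivolumab, the same section treats higher-grade elevations as a warning of immune-mediated hepatitis. If the exception is read as still in force, it has outlived both its rationale and the conditions that made it safe.

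**Working it through.** No sample size, power or error-rate figure is involved. The check is a comparison of texts, followed by a dating exercise for reach.

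**1. What the exception depended on.** For ALT/AST above 5 and up to 8 x ULN, Section 7.4.1.1 required a delay until Grade 1 or baseline, monitoring about every 3 days, and discontinuation if there was no improvement within 7 days. All of this is withdrawn.

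**2. What is left for isolated ALT/AST in Cycle 1.**

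| ALT/AST (x ULN) | If the exception lapsed | If the exception survives |
|---|---|---|
| > 3 to 5 | Delay | Delay |
| > 5 to < 8 | Permanent discontinuation | No stop and no tabled delay |
| 8 or more | Permanent discontinuation | Permanent discontinuation |

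In the last column the middle band is handled less strictly than the milder band above it. The table's row for other laboratory abnormalities cannot fill the gap, because it covers only abnormalities not already listed.

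**3. Does the banner settle it?** A missing mark proves nothing alone. The creatinine row also has an unmarked pointer: "See bempegaldesleukin-specific criteria in Table 7.4.1-2 for transient, non-inflammatory increased serum creatinine". The neurological row has a similar one. Both name bempegaldesleukin, so the banner disposes of them. The hepatic exception names neither drug. It refers to study treatment, which under Section 7.1 is now nivolumab alone. Amendment 04 did tag single items in this table, namely the pointer in the row for other drug-related AEs and footnote a.

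**4. Does Section 7.4.2 settle it?** Only in part. Its pointer to 7.4.1.1 concerns cytokine-type elevations and so probably lapsed. The nivolumab text that remains still sends only Cycle 2 onwards to the immune-mediated guidelines, which leaves Cycle 1 without a destination in that section.

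**5. Reach, by meaning of Cycle 1.** Tables 2-2 and 2-3 each label a Cycle 1. Assume the last randomization was on 14-Apr-2022, the date of the announced decision (the actual date is not given), and use the latest protocol windows.
- Neoadjuvant Cycle 1: first dose within 3 days = 17-Apr-2022; + 21 days = 08-May-2022. That is 33 days before Amendment 04 (10-Jun-2022), so barring dose delays nobody is affected.
- Adjuvant Cycle 1: third neoadjuvant dose at 17-Apr + 42 days = 29-May-2022; cystectomy within 42 days = 10-Jul-2022; adjuvant start 60 to 120 days later = 08-Sep-2022 to 07-Nov-2022. That is 90 to 150 days after the amendment, so some participants could be affected.

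**6. Why the limit to Cycle 2 onwards matters on the adjuvant meaning.** With three neoadjuvant doses on schedule, adjuvant Cycle 1 after surgery starts no earlier than 42 + 60 = 102 days from first dose, about 3.4 months. Section 7.4.2 gives a median onset of 3.3 months for the higher-grade nivolumab abnormalities. A cycle labelled 1 could then fall when immune-mediated hepatitis is to be expected.

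**The case against.** The strongest reply is that the documents favour one reading. The exception is not free-standing: it sends the reader to 7.4.1.1, which is titled for both drugs, is limited to the first cycle of the combination, and is withdrawn. The amendment's stated reason is that bempegaldesleukin will no longer be given. On that view the exception is bempegaldesleukin text, and what stays unchanged for nivolumab is the stop above 5 x ULN. The protocol also uses Cycle 1 Day 1 elsewhere as a single start of treatment (Sections 7.1.1 and 7.7.2.1), which favours the neoadjuvant meaning. This argument is sound as to probable intent and keeps the point minor. It does not remove the exception from the cell.

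The backstops also stand: delay on investigator judgement (Section 7.4), discontinuation for substantial clinical risk (8.1.1), the bilirubin and concurrent-elevation rules, and Appendix 6, which covers all immuno-oncology agents. The Appendix 6 hepatic figure is not reproduced in the available text, so no gap can be inferred from it; its footnote refers back to the protocol's own delay and discontinuation criteria.

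A reader might infer three stronger things. First, that the plan now permits redosing at 5 to 8 x ULN. It does not: the exception says only that discontinuation is not required. Second, that a definite number of participants is exposed, worked out from planned accrual. Actual accrual, the last randomization date and the incidence of isolated elevations in this band are not given, and any count would rest on the less supported adjuvant meaning of Cycle 1. Arm B, moreover, never received bempegaldesleukin, so the loss of the cytokine rationale changes nothing for that arm. Third, that monitoring frequency or efficacy results are affected. Nothing in the documents shows this.

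**Conclusion.** The point holds as a small leftover conflict in a safety table, of minor severity. The exception most likely lapsed with Section 7.4.1.1, but neither the wording of the cell nor the banner says so, and the literal reading leaves a more severe band with less instruction than a milder one. Only isolated ALT/AST above 5 and below 8 x ULN in Cycle 1 is touched. Reach is essentially nil if Cycle 1 means the first cycle of the combination. Otherwise it is confined to participants starting adjuvant Cycle 1 after the amendment. The dating rests on an assumed last randomization of 14-Apr-2022 and on-schedule dosing, and no headcount is claimed. The sponsor should confirm the intent.

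**What to change.** In the hepatic row of Table 7.4.1-1, mark the Cycle 1 exception not applicable per Protocol Amendment 04, so that ALT/AST above 5 x ULN means permanent discontinuation of nivolumab in every cycle. In Section 7.4.2, mark the pointer to 7.4.1.1 not applicable and delete the limit to Cycle 2 onwards, so that the immune-mediated hepatic guidelines apply to nivolumab in all cycles. If the sponsor instead meant the exception to survive, it would need to restate the withdrawn delay and 7-day stop and say which Cycle 1 is meant.

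The cost is one table cell and two phrases, by administrative letter or amendment, with no new procedures. The downside is that a few participants with transient elevations would stop nivolumab.

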7.4.2 Monitoring and Management of Elevated Hepatic Transaminases

Per Protocol Amendment 04, language for bempegaldesleukin is no longer applicable. Elevated hepatic transaminases are an overlapping toxicity that can occur for both bempegaldesleukin and nivolumab. The elevations in hepatic transaminases associated with bempegaldesleukin typically occur at the time of peak active cytokine concentration in the blood (Days 2-4), and are often accompanied by other cytokine-related toxicities such as flu-like symptoms, rash or pruritus. The transient elevations in hepatic transaminases are usually mild or moderate in severity, not associated with increased total bilirubin, resolve spontaneously without treatment, and predominantly occur in Cycle 1 and Cycle 2. Grade 3 laboratory abnormalities with these characteristics have been observed in PIVOT-02 during Cycle 1, and participants were able to continue study treatment uninterrupted with close laboratory monitoring. For transaminase elevations occurring in Cycle 1 consistent with a cytokine related effect without alternative etiologies, follow the Cycle 1 hepatic adverse event management guideline ([Section 7.4.1.1](#)).

Hepatic events, including elevated liver function tests, have also been observed for nivolumab. Most cases were of low or moderate severity. Higher grade abnormalities are concerning for immune-mediated hepatitis, and typically occur with a later onset (median time to onset of 3.3 months). Immune-mediated hepatitis generally results in a quick rise in liver function tests, and responds to corticosteroids or immune-modulating agents. For transaminase elevations occurring in Cycle 2 onwards potentially involving an immune-mediated mechanism, follow the immune-mediated hepatic adverse event management guidelines in the nivolumab Investigator's Brochure or product labeling for appropriate management.

7.4.3 Monitoring and Management of Bempegaldesleukin-induced Eosinophilia

This section is not applicable per Protocol Amendment 04. Frequent and significant eosinophilia has been observed in participants receiving both single agent bempegaldesleukin and bempegaldesleukin plus nivolumab, primarily starting at Cycle 2 or later, consistent with the known effect of IL-2 therapy. Clinical data analysis demonstrated that frequency of selected AEs (primarily Grade 1 or 2 in severity) such as rash, pruritus, edema, nausea, vomiting, diarrhea, and dizziness increased with level of eosinophilia. Isolated cases of suspected hypereosinophilic syndrome have been reported.

Absolute eosinophil count (AEC) should be closely monitored per protocol. If study participant is suspected to have hypereosinophilic syndrome (symptoms may involve skin, lungs, digestive tract, heart, blood and nervous system) with AEC at or above 5000/ μ L (5×10^9 /L) level, bempegaldesleukin treatment may need to be withheld, and the participant should be treated as clinically indicated.

7.4.4 Monitoring and Management of Adrenal Insufficiency and Hypophysitis

Adrenal insufficiency and hypophysitis have been observed in participants receiving nivolumab. Consider prompt evaluation when participants have signs or symptoms of hypophysitis or adrenal

insufficiency which includes levels of early-morning adrenocorticotrophic hormone (ACTH), cortisol, thyroid-stimulating hormone (TSH), and free thyroxine (T4). Co-management with an endocrinologist is recommended for participants with pre-existing adrenal insufficiency.

7.4.5 Management Algorithms for Immuno-oncology Agents

Per Protocol Amendment 04, the text below related to bempegaldesleukin is not applicable; however, the criteria remain unchanged for nivolumab. Immuno-oncology agents are associated with AEs that can differ in severity and duration from AEs caused by other therapeutic classes. Bempegaldesleukin and nivolumab are considered immuno-oncology agents in this protocol. Early recognition and management of AEs associated with immuno-oncology agents may mitigate severe toxicity. Management Algorithms (see [Appendix 6](#), [Appendix 7](#), [Appendix 8](#), and the nivolumab IB) have been developed to assist Investigators in assessing and managing the following groups of AEs:

- Gastrointestinal
- Renal
- Pulmonary
- Hepatic
- Endocrinopathy
- Skin
- Neurological
- Myocarditis
- CVA
- Cytokine-release Syndrome (CRS)

Advanced Cardiac Life Support (ACLS) and institutional guidelines should be followed for all CVA cases. For participants previously treated with bempegaldesleukin plus nivolumab who have experienced a CVA or TIA, the Investigator should discuss risk/ benefit of continuing nivolumab. A management algorithm for possible signs and symptoms of CVA or TIA for participants treated with bempegaldesleukin in combination with a checkpoint inhibitor is provided in Appendix 7 **(not applicable per Protocol Amendment 04)**.

7.4.5.1 Management Algorithm for Cytokine-release Syndrome

This section is not applicable per Protocol Amendment 04. CRS is a clinical diagnosis with a constellation of symptoms often characterized by fever, tachypnea, headache, tachycardia, hypotension, rash, and/or hypoxia caused by the release of cytokines. In addition, diarrhea and end organ dysfunction can be seen in CRS. Many of these symptoms overlap with known AEs seen in bempegaldesleukin and nivolumab combination therapy (ie, pyrexia and hypotension). These symptoms may be seen in infusion reactions as well as other known syndromes, such as tumor lysis syndrome and macrophage activation syndrome. For suspected CRS of Grade 3 or above, the

Investigator is encouraged to contact the Medical Monitor. An algorithm for the management of CRS is provided in [Appendix 8](#) (not applicable per Protocol Amendment 04).

